CVLT-II	California Verbal Learning Test – Second edition
DMD	Disease Modifying Drug
EAIR	Exposure adjusted incidence rates

CCI

ET	Early Termination
FAS	Full Analysis Set

CCI

HRQOL	Health Related Quality of Life
ICH	International Conference on Harmonization
IA	Interim Analysis
IAP	Integrated Analysis Plan
iRT	Interactive Response Technology
ITT	Intention to Treat

CCI

LS	Least Square
MCID	Minimally Clinically Important Difference

MedDRA	Medical Dictionary for Regulatory Activities
MRI	Magnetic Resonance Imaging
NA	Not Applicable
NCI-CTCAE	National Cancer Institute – Common Terminology Criteria for Adverse Events
MRI	Magnetic Resonance Imaging
MS	Multiple Sclerosis
MSQoL-54	Multiple Sclerosis Quality of Life-54 Questionnaire

CCI

eCRF	electronic Case Report Form
ePRO	electronic Patient Reported Outcomes
PBVC	Percentage brain volume change
PD	Protocol Deviation
PDGMVC	Percentage deep grey matter volume change
PGMVC	Percentage grey matter volume change
PML	Progressive Multifocal Leukoencephalopathy
PT	Preferred Term
PWMVC	Percentage white matter volume change
SAE	Serious Adverse Event
SAF	Safety Analysis Set
SD	Standard Deviation
SDMT	Symbol Digit Modalities Test
SDTM	Study Data Tabulation Model
SF-36	36-Item Short Form Health Survey
SOC	System Organ Class

CCI

TCS-1	Treatment Completer Set – Year 1
TCS-2	Treatment Completer Set – Year 2
TEAE	Treatment Emergent Adverse Event
TLF	Tables, Listings, and Figures
TSQM v1.4	Treatment Satisfaction Questionnaire Medication version 1.4

WHO-DD **World Health Organization Drug Dictionary**

CCI

CCI

CCI

4

Purpose of the Integrated Analysis Plan

The purpose of this Integrated Analysis Plan (IAP) is to document technical and detailed specifications for the interim and final analyses of data collected for protocol MS700568_0021. Results of the analyses described in this IAP will be included in the Clinical Study Report (CSR). Additionally, the planned analyses identified in this IAP may be included in regulatory submissions or future manuscripts. Any post-hoc, or unplanned analyses performed to provide results for inclusion in the CSR but not identified in this prospective IAP will be clearly identified in the CSR.

The IAP is based upon Section 8 (Statistics) of the study protocol and protocol amendments and is prepared in compliance with ICH E9. It describes analyses planned in the protocol and protocol amendments. The IAP specifies also a 1-year interim analysis, which is not planned in the protocol, and any additional analysis to describe the potential impact of the COVID-19 pandemic. Also, an additional Baseline analysis was performed, which is not mentioned in the protocol, and will be described and reported separately.

5 Objectives and Endpoints

	Objective	Endpoint	IAP section
Primary Objective	To assess the health-related quality of life (HRQoL) through the MSQoL-54 scale in highly-active relapsing multiple sclerosis (RMS) subjects treated with Mavenclad® for 2 years (24 months).	Primary Endpoint • Changes in MSQoL-54 at 24 months compared to Baseline, i.e. the changes in the physical and mental health composite scores.	14.1
Secondary Objective	To assess treatment satisfaction through the Treatment Satisfaction Questionnaire Medication (TSQM) v1.4 questionnaire in highly active RMS subjects at 6 months of treatment with Mavenclad®.	Secondary Endpoint • Treatment global satisfaction assessed by TSQM v1.4 at 6 months.	0

6 Overview of Planned Analyses

The following analyses are planned for the study:

- Interim analysis (IA) after all subjects have completed the 6-month assessment,
- IA after all subjects have completed the 1-year (Month 12a Visit) assessments,
- Final analysis at the end of the study.

The 1-year IA is not specified in the protocol. The approval to perform the unplanned IA was given 30 July 2020.

In addition, a Baseline analysis was performed. This Baseline analysis is not specified in the study protocol and is described in a separate Analysis Plan.

6.1 Interim Analysis

6.1.1 6-month Interim Analysis

An interim analysis will be undertaken after all subjects have completed the 6-month assessment. As the primary endpoint is not available at this time, the interim analysis will focus on the secondary endpoint which is the treatment global satisfaction assessed by TSQM v1.4 at Month 6 Visit which will be analyzed with a mixed linear regression model overall and by the subgroup, “Previous treatment with Disease Modifying Drugs (DMDs)”, see Section 0 for details.

The interim analysis will be considered as supportive of the 24-month analysis (final analysis). Due to the exploratory nature of the study, no alpha spending was planned to control for overall type-I-error inflation.

In addition, the Interim Analysis will describe the following characteristics of the study population:

- Disposition (Section 10.1) including and up to the cut-off point,
- Baseline Characteristics including MS Disease Characteristics (Section 11),
- Relevant Previous Medications (Section 12),

and will include the following endpoints:

- Treatment Effectiveness, Side effects, and Convenience assessed by TSQM v1.4 at the Month 6 Visit (Section 0),
- Changes in level of disability as measured by CCI ██████████ at the Month 6 Visit compared to Baseline (Section 14.3),
- Relapse reports including and up to the cut-off point (Number and Percentage of Subjects with (qualifying) relapses),
- Occurrences of TEAEs and SAEs as well as Lymphocyte counts including and up to the cut-off point (Section 15).

The characteristics will be summarized descriptively up to Month 6 Visit in the same way as for the final analysis.

Table 1 lists all assessments which will be included in the interim analysis.

Table 1: List of assessments included in the interim analysis

Assessments	Screening	Baseline	Month 2	Month 6
Informed Consent	X			
Demographic	X			
iRT		X		
Disease History	X			
CCI				
Lymphocyte Count	X	X	X	X
Treatment Satisfaction (TSQM v1.4)				X
Treatment Administration		X		
Relapse Report			X	X
AEs		X	X	X
Treatment and Study Termination		X	X	X
Relevant Previous Medication	X			

Cut-off date

Only data up to the Month 6 Visit of each subject will be analyzed in the interim analysis. Therefore, the cut-off date is defined as the maximum Month 6 Visit date (i.e. date of the last assessment for the Month 6 Visit). For subjects with a missing Month 6 Visit the cut-off date will be 180 days after start of study medication. This includes subjects who discontinued before Day 180.

- Cut-off date (Month 6 Visit done) = Maximum Month 6 Visit date
- Cut-off date (Month 6 Visit not done) = Start of study medication + 180 days

All events of death will be included in the interim analysis regardless of the timepoint (i.e. any death that is included in the database at the time of the snapshot will be reported in the interim analysis).

All data included in the IA will undergo a data cleaning process, however, as the key data point is an ePRO and no decisions on further study conduct are based on this IA, it is not required to have all data 100% cleaned. The quality of the data will be reviewed during the Data Review Meeting.

Data handling after cut-off date

Data after cut-off do not undergo the cleaning process.

Data other than the date of death obtained after the cut-off will not be displayed in any listings or used for summary statistics.

If the stop date for an AEs is after the date of cut-off, the AEs will be considered as ongoing during the Interim Analysis.

6.1.2 1-year Interim Analysis

A second unplanned IA will be undertaken after all subjects have completed the initial 12-month assessment.

The interim analysis will focus on the new defined tertiary endpoint, the change in Multiple Sclerosis Quality of Life-54 (MSQoL 54) physical and mental health composite scores at the Month 12 Visit compared to Baseline, which will be analyzed applying the same methodology as specified for the primary endpoint the MSQoL 54 at Month 24 (see section 14.1 for details) except for the repeated visit effect as there is only one post-baseline assessment in this analysis. As a sensitivity analysis, the analysis will be repeated by the subgroup “Previous treatment with DMDs” (Section 8.2). In order to evaluate a potential impact of the Coronavirus disease 2019 (COVID-19) pandemic on the QoL of patients, the analysis will also be repeated by a subgroup of patients that had their Month 12 MSQoL assessment after the start of the COVID-19 pandemic versus patients that had their results already reported before this date.

Analysis (Analysis Set)	Derivation	Statistical Analysis Methods	Missing data handling
CCI			

As this IA is unplanned, no alpha spending was planned to control for overall type-I-error inflation and no stopping rules or any other modifications to the study are defined with this IA.

In addition, the Interim Analysis will describe the following characteristics of the study population:

- Disposition (Section 10.1) including and up to the cut-off point,
- Summary of visits / MSQoL assessments performed before and after start of COVID-19 pandemic,
- Baseline Characteristics including MS Disease Characteristics and results from the central MRI review for the screening MRI (Section 11),
- Relevant Previous Medication (Section 12),

and will include the following endpoints:

- Change in MSQoL Overall quality of life at the Month 12 Visit compared to Baseline (Section 14.3.1)
- Global satisfaction, Treatment effectiveness, Side effects, and Convenience assessed by TSQM v1.4 at the Month 6 and Month 12 Visit (Section 14.3.2),
- Changes in level of disability as measured by EDSS, at the Month 6 and Month 12 Visit compared to Baseline (Section 14.3),
- Relapse reports including and up to the cut-off point (number and percentage of subjects with (qualifying) relapses),
- Occurrences of TEAEs and SAEs as well as Lymphocyte counts including and up to the cut-off point (Section 15).

These characteristics will be summarized descriptively up to Month 12a Visit in the same way as for the final analysis. In addition, all TSQM scores will be analyzed applying the repeated mixed-effects linear regression as specified in Section 14.3.2 (apart from the inclusion of the Visit effect for Month 24). MSQoL and selected disposition and Baseline analyses will be repeated by subgroup “Month 12 MSQoL assessment after start of COVID-19 pandemic”.

Table 2 lists all assessments which will be included in the 1-year interim analysis.

Table 2: List of assessments included in the 1-year interim analysis

Assessments	Screening	Baseline	Month 2	Month 6	Month 12a
Informed Consent	X				
Demographic	X				
iRT		X			
Disease History	X				
CCI					
MSQoL-54		X			X
MRI	X				
CCI					
Lymphocyte Count	X	X	X	X	X
Treatment Satisfaction (TSQM v1.4)				X	X

Assessments	Screening	Baseline	Month 2	Month 6	Month 12a
Treatment Administration		X			
AEs		X	X	X	X
Treatment and Study Termination		X	X	X	X
Relevant Previous Medication	X	X			

Cut-off date

Only data up to and including the Month 12a Visit of each subject will be analyzed in the IA. Therefore, the cut-off date is defined as the maximum Month 12a Visit date (i.e. date of the last assessment for the Month 12a Visit). For subjects with a missing Month 12a Visit the cut-off date will be 360 days after start of study medication. This includes subjects who discontinued before Day 360.

- Cut-off date (Month 12a Visit done) = Month 12a Visit End Date (i.e. Maximum Month 12a Visit date)
- Cut-off date (Month 12a Visit not done) = Start of study medication + 360 days -1

Any assessments from the Month12b or later Visits will not be included in the IA, however, any events or concomitant medications reported during these visits that have an onset/start date before or at the cut-off date will be included.

All events of death will be included in the interim analysis regardless of the timepoint (i.e. any death that is included in the database at the time of the snapshot will be reported in the interim analysis).

All data included in the IA will undergo a data cleaning process, however, as the key data point is an ePRO and no decisions on further study conduct are based on this IA, it is not required to have all data 100% cleaned. The quality of the data will be reviewed during the Data Review Meeting.

Data handling after cut-off date

Data not included in the 12 month IA do not undergo the cleaning process.

Data other than the date of death obtained after the cut-off will not be displayed in any listings or used for summary statistics.

If the stop date for an AEs is after the date of cut-off, the AEs will be considered as ongoing during the Interim Analysis.

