This subgroup is used in 1-year IA and any ePRO analyses dedicated to 1-year data as specified in the respective sections.

Specific analyses as specified in the respective sections will be repeated for these subgroups.

9 General Specifications for Data Analyses

Treatment groups

The treatment group will be labeled as Mavenclad®.

Significance level

All statistical tests mentioned in this IAP are to be regarded as exploratory. All statistical tests will be performed 2-sided. If confidence intervals are to be calculated, these will be 2-sided with a confidence probability of 95%, unless otherwise specified in this IAP.

Presentation of continuous and qualitative variables

Continuous variables will be summarized using descriptive statistics, i.e. number of subjects, number of subjects with missing and non-missing values, mean, standard deviation, median, 25th Percentile - 75th Percentile (Q1-Q3), minimum, and maximum.

Qualitative variables will be summarized by counts and percentages.

Unless otherwise stated, the calculation of proportions will be based on the number of subjects of the analysis set of interest. Therefore, counts of missing observations will be included in the denominator and presented as a separate category.

In case the analysis refers only to certain Visits percentages will be based on the number of subjects still present in the study at that Visit, unless otherwise specified.

Definition of Baseline

The last non-missing measurement prior to start of study medication will serve as the Baseline measurement. Measurements performed on the day of first intake of study medication are assumed to be “prior to start of study medication” as long as it has not been confirmed that the procedure was performed afterwards. This assumption is justified as following the sequence of procedures as specified in the study protocol. The intake of study medication should be the last procedure on the visit day.

Definition of change from Baseline

Change from Baseline = Visit value – Baseline value

Percent Change from Baseline = $100 * (Visit value - Baseline value) / Baseline value$

Definition of visit dates

The visit start date is the date of the first assessment which belongs to the corresponding visit.

The visit end date is the date of the last assessment which belongs to the corresponding visit.

Definition of duration

Duration will be calculated by the difference of start and stop date + 1 in days (if not otherwise specified).

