14.1.1 Primary Objective: Analysis of the primary endpoints

The primary objective is to assess the HRQoL through the MSQoL-54 scale in highly active RMS subjects treated with Mavenclad® for 2 years (24 months).

The primary endpoints for the study are the changes in HRQoL assessed by MSQoL-54 physical health and mental health at 24 months post-Baseline assessment. Differences in MSQoL-54 scores between measurements at the Month 24 Visit and Baseline will be assessed using repeated mixed-effects linear regression, accounting for clinically relevant factors, within subject correlation and within pooled center correlation.

As the analysis set concerns repeated measurements for outcomes for each individual, it is likely that observations pertaining to each individual will be correlated. Furthermore, as this is a multi-center study, it is likely that clustering of individuals within study sites will produce an additional source of correlation. Mixed-effects regression, whereby a three-level hierarchical model is specified for observations within subjects within-pooled centers, will be used to account for within-subject and within-pooled center correlation (Gibbons et al., 2010).

The analysis will also adjust for factors deemed to be prognostic for the primary endpoint, as judged by clinical experts. These factors are the age and EDSS at Baseline, (see Section 9 for details).

The primary endpoints are the changes from Baseline to Month 24 Visit in Physical and Mental health composite of the MSQoL-54. They will be analyzed with a repeated mixed-effects linear model for change from Baseline that will take all planned intermediate measurements into account whereby a three-level (visits within subjects within centers) hierarchical model is specified for repeated MSQoL-54 Physical or Mental health composite scores.

$$Y = X\beta + \gamma + e, \text{ where}$$

Y represents change from baseline in MSQoL score,

X represents values of fixed effects including MSQoL score, age and EDSS at Baseline, and Visit (defined as a class variable),

β represents set of regression coefficients,

γ represents pooled center random effect,

e represents a random error, potentially correlated for different visits within a subject (nested within a center).

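### The readable SAP evaluates pandemic impact on Month 12 QoL by repeating the change-from-Baseline model by COVID-19 subgroup and states no estimate of the difference between subgroups

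*SAP*

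**What the plan says.** The aim is in SAP 6.1.2 (1-year Interim Analysis): "In order to evaluate a potential impact of the Coronavirus disease 2019 (COVID-19) pandemic on the QoL of patients". The method follows in the same sentence: "the analysis will also be repeated by a subgroup of patients that had their Month 12 MSQoL assessment after the start" of the pandemic, "versus patients that had their results already reported before this date". Later in 6.1.2 the instruction recurs: "MSQoL and selected disposition and Baseline analyses will be repeated by subgroup", naming the COVID-19 subgroup.

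The model to be repeated is the one for Month 12 change in the physical and mental health composites, obtained by "applying the same methodology as specified for the primary endpoint" but without the repeated visit effect. SAP 14.1.1 defines that model: "X represents values of fixed effects including MSQoL score, age and EDSS at Baseline, and Visit (defined as a class variable"), plus a random pooled-center effect. Its hypotheses set the population mean change of each composite to zero, and it reports LS means, standard errors, 95% CIs and two-sided p-values.

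SAP 8.2 classes a subject as Yes or No by the date of the Month 12 MSQoL assessment, and adds: "This subgroup is used in 1-year IA and any ePRO analyses dedicated to 1-year data". SAP 9 sets the pandemic start country by country, no later than 11 March 2020.

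The table in 6.1.2 with a column for statistical methods is blacked out below its headings, as is text after 14.1.1.

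**The concern.** Whether the pandemic affected quality of life is a question about a difference: was the mean change in subjects assessed after the start equal to that in subjects assessed before it? The readable method fits a model to each subgroup and tests a different null in each, namely that the subgroup's own mean change is zero. The listed fixed effects contain no COVID-19 term, and no contrast between the subgroups is named.

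If the results are laid out as two p-values, the natural temptation is to read significance in one subgroup and not in the other as a pandemic effect, and significance in both as no effect. Neither inference is sound. SAP 4 sends results to the clinical study report and allows their use in regulatory submissions and manuscripts. SAP 6.2 carries all described analyses except the Month 6 TSQM model into the final analysis. The output may therefore be read well beyond the interim report.

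**Working it through.** **No figure to reproduce.** The readable text gives no power or precision for this analysis. The protocol plans 445 subjects; the SD of change and the share assessed after the pandemic start are not readable.

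**Inputs.** From the documents: two-sided tests (SAP 9) and a nominal 0.05 level (protocol 8.5.1). Assumed: 400 subjects with Month 12 data; SD of change 15, varied from 12 to 18; splits of 50/50, 30/70 and 20/80; the same true mean change d in both subgroups (no pandemic difference), in whole points from 0 to 4. Covariates and center clustering are ignored.

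**Formulas.**
- Power within subgroup i: p_i = Φ(d/SE_i − 1.96) + Φ(−d/SE_i − 1.96), with SE_i = SD/√n_i.
- Probability that exactly one subgroup is significant: p1(1 − p2) + p2(1 − p1).
- Direct contrast: SE = SD·√(1/n1 + 1/n2); 95% CI half-width = 1.96·SE; false-positive rate 5%.

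**Two cells in full, d = 2, SD 15.**
- 50/50: SE = 15/√200 = 1.061 in each subgroup, so p = 0.470 in each. Discordance = 2 × 0.470 × 0.530 = 0.498.
- 20/80: SEs are 15/√80 = 1.677 and 15/√320 = 0.839, giving p = 0.222 and 0.665. Discordance = 0.222 × 0.335 + 0.665 × 0.778 = 0.59.

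**Probability that exactly one subgroup is significant when there is no difference (SD 15).**

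| Common change (points) | 50/50 | 30/70 | 20/80 |
|---|---|---|---|
| 0 | 9.5% | 9.5% | 9.5% |
| 1 | 26% | 27% | 27% |
| 2 | 50% | 54% | 59% |
| 3 | 31% | 42% | 56% |
| 4 | 6.8% | 17% | 34% |

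Over SD 12 to 18 the same grid runs from 0.6% (SD 12, 50/50, 4 points) to about 62% (20/80, at 2 points with SD 12 or 3 points with SD 18). The figure is small when both subgroups are strongly powered and large when power is intermediate or unequal.

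**Check in SD units with the planned 445.** At a common change of 0.15 SD, discordance is 48%, 55% and 63% for the three splits. At 0.30 SD it is 1.2%, 6.6% and 19%. The pattern is the same.

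**A real difference.** Take true changes of +8 before and +4 after, 50/50, SD 15. Within-subgroup powers are above 0.999 and 0.965, so exactly one is significant only 3.5% of the time. The direct contrast has SE = 15·√(2/200) = 1.5, 4/1.5 = 2.67, and power 76%.

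**Precision of the direct contrast (SD 15).** SE is 1.50, 1.64 and 1.875 for the three splits, so half-widths are 2.9, 3.2 and 3.7 points.

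**The case against.** **The redaction.** The table that would hold the method for this analysis is blacked out, and the sentence sets one group against the other with a "versus". A contrast may be specified there. This stands: a reader might infer that the plan contains no between-subgroup test at all, and the documents cannot support that. The point is limited to the readable text. The word itself names two groups but no estimate or test.

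**The p-values are not the only output.** LS means, standard errors and CIs are also reported, so a reader could form an approximate difference by hand. In the +8/+4 example each mean would carry a CI of about ±2.1 (1.96 × 1.061), and the gap would be visible. This also stands. Nowhere does the SAP say that pandemic impact will be judged by discordant significance. The table above shows what that reading would cost; it is not an error rate of a planned rule. But if the difference is the quantity of interest, the plan should report it with its own interval.

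**Low stakes.** SAP 4 and 7 speak of describing the pandemic's potential impact, all tests are exploratory, and no decision on conduct depends on this interim analysis. That limits the consequences and excuses the lack of multiplicity control. It does not make a within-subgroup null answer a between-subgroup question.

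**Previous DMD treatment and TSQM.** It is tempting to extend the criticism to the DMD subgroup, where Month 6 treatment satisfaction is "analyzed with a mixed linear regression model overall and by the subgroup" of previous treatment. The documents do not support this. SAP 6.1.2 calls the DMD repeat a sensitivity analysis and states no comparative aim, and TSQM is not collected at Baseline, so its Month 6 model is not a change-from-Baseline model.

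**Confounding.** Subgroup membership follows calendar date and country, so even a direct contrast cannot isolate a pandemic effect. This stands and shapes the fix.

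**Conclusion.** The concern holds for the COVID-19 subgroup in SAP 6.1.2, on the readable text. The aim is comparative; the stated method repeats a model whose p-values test mean change equal to zero; and no difference, interval or test between subgroups can be read.

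Relying on the two p-values would mislead to a degree that depends on unknowns. At SD 15 and 400 subjects the chance of a spurious contrast runs from about 7% to 59% over whole-point changes of 0 to 4, against 5% for a direct comparison. Sample size, SD, split and common change are all assumptions.

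The documents support neither the claim that no contrast exists anywhere in the plan nor the claim that significance in one subgroup alone is the planned criterion. The matter is confined to exploratory 1-year data and leaves the Month 24 primary analysis untouched.

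**What to change.** First check the redacted methods table in SAP 6.1.2. If it already specifies a between-subgroup estimate, state it in the text and nothing more is needed.

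If not, amend 6.1.2 as follows, and apply it wherever the COVID-19 subgroup is used for Month 12 MSQoL-54:

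- Fit one Month 12 model per composite on all subjects, with the COVID-19 subgroup (after or before) as a fixed factor alongside Baseline score, age, EDSS category and pooled center.
- Report the after-minus-before difference in LS mean change with its 95% CI as the main result.
- Keep the within-subgroup LS means as description.
- State that the difference is a non-randomised association, because membership depends on enrolment timing and country.

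The cost is one model term, one estimate statement and a few lines of SAP wording, with no new data. The drawback is a wide interval, about ±2.9 to ±3.7 points at the assumed SD of 15, which should be shown as it is.
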